1.0 BACKGROUND AND RATIONALE

1.1 Study Synopsis

This is a single center, two-arm pilot randomized controlled trial (RCT) evaluating the feasibility and acceptability of a novel psychosocial intervention, Families Addressing Cancer Together (FACT) delivered as a mobile response web application (mobile web app). FACT is a theory-guided, psychoeducational intervention designed to improve parents' confidence and ability to talk about their cancer with their minor children. We will enroll 40 patients with cancer who have a minor child to participate in this 6-week study. The primary hypothesis being tested is that an intervention that assists parents with their communication needs with their children can be feasible, acceptable, and improve parental communication self-efficacy when compared with a waitlist control condition. Findings from this study will inform a future grant application to further test this intervention in a randomized full efficacy trial.

1.2 Background

Parents with cancer are encouraged to be “honest and open” with their minor children about their illness. Yet, for the nearly two million US parents facing a new cancer diagnosis and treatment,¹ most will receive minimal guidance from their oncology or psychosocial oncology providers for this difficult task. For parents with cancer, the disease creates major disruptions to the family unit, threatens parents’ desire to protect their children from harm, and leads to substantial depression and anxiety.^{2,3} Concerns about communication with children contribute to this heightened distress: parents report uncertainty about what to tell their children, the optimal timing of disclosure, and how to provide developmentally appropriate, emotionally-charged information.^{4,5} For parents with advanced disease, discussing life-limiting prognoses are particularly challenging. Parental communication about illness is linked to better emotional adjustment for both themselves and their children,⁶⁻⁸ yet most cancer centers lack the resources to address these patients’ needs. Lay publications to support parental illness communication exist, but patients prefer tailored resources specific to their concerns and disease.^{9,10}

The few evidence-based interventions to facilitate parental cancer communication demonstrate high acceptability, yet are limited by the need for extensive infrastructure or highly specialized providers, thus limiting dissemination. What remains unknown is how to deliver timely, customized parental communication guidance across cancer treatment settings. Without this support, parents with cancer and their children experience avoidable psychosocial distress. In order to better support parental communication needs in cancer, psychosocial interventions that can be implemented across clinical practice settings are needed.

To address this gap, we have developed FACT – a theory-guided, psycho-educational intervention to help parents with cancer talk about their illness with their children in a developmentally appropriate way. We designed FACT to be responsive to parents’

concerns and communication goals and to support nuanced communication that considers parents' disease, treatment, prognosis, and maturity of their child. FACT accomplishes this customization via computer-tailored algorithms and >1000 message library. Parents complete a separate tailoring assessment for each child, allowing FACT to generate child-specific content. FACT pairs educational content with conversation scripts ("words you can use") –user-tested examples for introducing complex or emotionally intense information. As a mobile responsive web application, FACT can be used with a variety of devices.

FACT was developed through an extensive review of the scientific literature and publicly available resources, consultation with mental health, social work, oncology, and palliative care clinicians, patient and caregiver stakeholder interviews, and data from the PI's prior observational studies with parents living with cancer.

1.3 Purpose and Rationale

This pilot study will provide the necessary data to inform the development and full efficacy testing of a novel psychosocial intervention to support parents with cancer in communicating with their children about cancer. The research questions to be answered by this study are whether the intervention being tested can be feasible, be acceptable, and provide preliminary estimates of improvement in parental communication and psychological outcomes as compared to a waitlist control condition.

2.0 STUDY OBJECTIVES

[figure not shown]
2.1 Primary Objective

The primary objective of this study is to evaluate the acceptability of FACT when delivered as a mobile web app. Acceptability will be defined through participant satisfaction ratings and analysis of semi-structured interview data.

2.2 Secondary Objective

A secondary objective of this study is to evaluate the feasibility of the study and study procedures in preparation for a future efficacy RCT of the intervention. We will report on participant screening, recruitment, and retention.

2.3 Exploratory Objectives

3.0 PATIENT ELIGIBILITY

3.1 Inclusion Criteria

Confirmation of eligibility criteria is required for all potential study participants prior to study enrollment. Participants will be eligible for study participation as defined by the inclusion and exclusion criteria as follows:

- 3.1.1. Informed consent reviewed and signed;
- 3.1.2. Age equal to or above 18 years;
- 3.1.3. Ability to understand and comply with study procedures;
- 3.1.4. Able to complete all study measures and visits in English;
- 3.1.5. Be a parent (defined as biological, adoptive, foster, or step-parent), kin caregiver (defined as a relative or someone with a significant emotional relationship who provides full-time care and nurturing of a child), or legal guardian of a child age 3 to 17 years of age who can speak and understand English;
- 3.1.6. Have a diagnosis of Stage II-IV (or equivalent) invasive solid tumor not in surveillance or survivorship

[figure not shown]
3.2 Exclusion Criteria

Eligible participants must not have any of the following to be enrolled in the study.

- 3.2.1. Unable to complete self-report instruments due to illiteracy, neurologic illness, inability to speak or read English, or other causes;
- 3.2.2. Prior participation in the pilot trial (LCCC2030) or development and user testing protocol (LCCC1952) preliminary to this study;
- 3.2.3. No current or expected contact with their child; or
- 3.2.4. Existence of other co-morbid disease, which in the opinion of the investigator, prohibits participation in the protocol.

4.0 STUDY PLAN

4.1 Schema

This is a two-arm, randomized controlled trial of 40 patients with cancer who are parents of minor children. Participants will be approached in hospital or clinic settings, complete

baseline assessments, randomized to intervention (FACT) vs. control (waitlist control), and complete follow-up assessments 3-weeks post-randomization and 6-weeks post-randomization. Study visits will occur at NCCH, via telephone, or secure video. We anticipate enrolling participants over a six-month period and that active participation will last for a 2-month period.

4.2 Duration of Study

The duration of individual participation is estimated to be two months per participant. Individual study participation is expected to consist of enrollment, baseline assessment, assignment to treatment arms, and two follow-up assessments inclusive of surveys and a semi-structured interview.

4.2.1 Baseline assessment (T0):

Based on our prior survey-based research studies, we anticipate the baseline assessment questionnaire to last approximately 10-15 minutes.

4.2.2 Treatment assignment:

Participants assigned to the study intervention will receive access to the online portal within which they can create and review their customized communication guidance. We anticipate that the creation process will last 5-10 minutes. Participants' access will be maintained throughout the course of their participation; as such, duration and frequency of active interaction with intervention assessments will be completely at the discretion of each individual participant.

4.2.3 3-week follow-up assessment (T1):

The 3-week post-intervention assessment consists of structured surveys, which we estimate will take approximately 10-15 minutes.

4.2.4 6-week follow-up assessment (T2):

The 6-week post-intervention assessment consists of structured surveys and a semi-structured interview with each participant to provide feedback on the intervention (if assigned to the treatment arm) and study procedures (both arms). The interview is expected to last approximately 30 minutes. The surveys will take approximately 10-15 minutes.

4.3 Study Details

4.3.1 Pre-study Assessments

4.3.1.1 Screening

We will use the screening procedures in place for [name] LCCC2030 study, "A Pilot Study of the Families Addressing Cancer together (FACT) Tool." Potential study participants will be identified through conversations with the participant's attending oncologists or Comprehensive Cancer Support Program (CCSP) consulting clinicians, review of outpatient multidisciplinary and hematology/oncology clinic patient rosters, review of radiation oncology and chemotherapy infusion room rosters and review of inpatient oncology service rosters or oncology consultation service rosters. We will request a waiver of HIPAA authorization to conduct this screening because of the high percentage of patients with cancer at UNC who might not be eligible for the study due to their age or disease status.

4.3.1.2 Recruitment and informed consent

The PI and other members of the research team will identify eligible patients through electronic medical record (EMR) review and receive permission from the patient's oncology clinician(s) before approaching eligible patients. As such, patients whom the oncology team believes are at high risk of emotional distress from study participation will not be approached. All participants will provide informed consent for the study and HIPAA authorization. Copies will be given to participants, and signed forms will be kept locked in the office of the PI or study coordinator. When approaching an eligible patient, the research team member will describe the nature of the study questions and their purposes and written or electronic informed consent will be sought.

When the treating oncology team believes it may be more acceptable to an individual patient, a member of the oncology team may first introduce the study. The provider will briefly describe the study, provide an approved brochure to the patient, and assess willingness to be contacted by the study team.

In addition to in-person recruitment, recruitment will occur by telephone. This method of recruitment will be used to recruit potential participants when in-person recruitment is unfeasible or restricted (e.g., due to COVID-19). This method will also be used to recruit potential participants who express interest in the study but who do not provide written or electronic informed consent at the time of initial in-person recruitment. As with in-person recruitment, telephone recruitment will only occur after receiving healthcare clinician permission to approach the patient and verbal statements from the patient that the study team can call them to further discuss the study. Patients who cannot be reached by phone after three attempts will receive an email, if applicable, from the study team. The content of any such email will be limited such that only the following information will be disclosed: the caller's name, that he/she/they is calling to follow up about a UNC research study, and staff contact information.

Participation in this study is voluntary. Patients who choose not to participate in this study will not be subject to prejudice in the delivery of health care by their physicians and clinical staff nor by the research institution. The informed consent discussion will occur with a trained member of the research team and will include review of the purpose of the

research, procedures, risks, benefits, and participant's rights. Study participants can contact the PI to address all questions both prior to and after consenting to participate in the study. All participants will be specifically reminded that they may withdraw at any time without impacting their treatment or relationship with their clinical team and that they may choose not to answer any study questions they would rather not answer, with exception to the tailoring questionnaire items used to generate their intervention materials.

Items in the tailoring questionnaire will be forced-response, as missing items would result in the study intervention being unable to generate participants' materials. Participants will be told during the informed consent process that those specific items will be forced-response, will have the opportunity to preview the items before consenting if desired, and will be informed as to the rationale for making these items forced-response. The consenting study team member will reaffirm that all other study questions may still be skipped if preferred.

4.3.2 Study assessments

4.3.2.1 Baseline study assessment (T0)

After receiving consent, each participant will be assigned a unique and random study ID. All data collected will be associated only with this ID. The research team member will then obtain baseline assessment information from the participant. Participants will complete the study forms online via a secure REDCap link or with pen and paper.

The baseline study assessment consists of a demographic form and several patient-reported outcome measures. See the Study Measures section and Appendices for details about the measures and how they will be administered. Baseline assessments must be completed before randomization.

4.3.2.2 Randomization

Participants will be randomized to one of two arms: (1) intervention arm, or (2) control arm. Participants will be assigned with an allocation ratio of 1:1 and stratified by disease status: advanced (stage IV or equivalent) vs non-advanced. This will be implemented through REDCap's randomization module which will directly follow entry of baseline data. Setup of the randomization module will be done only by the PI or CRC, and the study biostatistician will confirm that the randomization scheme logic is functional before any data is collected. This logic will be preserved such that group assignment cannot be altered or manipulated when accrual begins.

Given the nature of this study, a double-blind design is not possible as both the participants and recruiting staff will be able to easily infer group assignment.

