7.0 STATISTICAL CONSIDERATIONS

7.1 Study Design

This is a two-arm pilot RCT testing the acceptability, feasibility, and preliminary evidence of efficacy for a novel communication intervention for parents with cancer.

The primary objective of acceptability will be measured using the 6-item satisfaction survey. Total scores range from 0-18, so a score of 12 or higher will be considered "acceptable". If the percentage of patients who report the intervention is acceptable is 75% or higher, the intervention will be considered for future testing.

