7.2 Sample Size and Accrual

We will recruit 55 patients over 6 months for the proposed study, with the hope of at least 20 patients completing T1 measures. A 95% exact binomial confidence interval (CI) will

be reported for the acceptability rate (only in the intervention group), and with n=20, the CI will have precision no more than +/- 23%. If the rate is 75%, the CI will be 50.9%, 91.3%).

For qualitative interview data, sample size estimation is based on projections of the number of participants needed to reach saturation of the concept. The sample size for the proposed study is adequate for qualitative analysis and consistent with psychosocial intervention development.^{18,19}

We are confident we have adequate access to the proposed sample during the study time frame. In 2019, NCCH records included 522 English-speaking adults ages 22-54 years with a stage IV solid tumor. Our screening records suggest ~60-70% NCCH patients in this age range are parents of minor children. Data from epidemiologic studies indicate that an estimated 30% of all adult breast cancer patients are parents of minor children.¹

Based on the PI's other research studies with parents with cancer, we conservatively expect to recruit, consent, and enroll ~10 patients/month for six months. The number of eligible patients per month is higher, however we consider factors that typically lead to deferred enrollment/consent such as patient fatigue, clinic scheduling delays, and intervening medical events.

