7.3.4 Explore impact of intervention on target outcomes

We will report on changes in CSES scores from pre- (T0) to post-intervention (T1, T2) . This pilot study is not designed nor powered to detect differences as the primary objectives are to evaluate the acceptability and feasibility of the intervention as compared to treatment as usual.

We will also report on changes in other patient-reported outcomes of interest including GAD-7 and PHQ-2 scores.

We will use descriptive statistics to report on the percentage of patients who engage in any communication behaviors about cancer with their children, the depth of their discussion, and their assessments of how their children responded to these conversations.

Data from this study will be used for preliminary estimates (for which the CSES will be the primary outcome measure) to power a future R01 testing the intervention. The projected effect size will be based on mean differences in SD for the CSES from this pilot study.

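### The PI may set up the randomisation module and also identifies eligible patients, and the stated safeguards do not stop someone with setup access from foreseeing assignments

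*Combined protocol and SAP*

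**What the plan says.** Section 4.3.2.2 describes 1:1 allocation, stratified by advanced or non-advanced disease, through REDCap's randomisation module. On who builds it: "Setup of the randomization module will be done only by the PI or CRC". Before data collection the study biostatistician checks that the scheme works. Once accrual starts, the protection is: "This logic will be preserved such that group assignment cannot be altered or manipulated when accrual begins". Randomisation comes directly after baseline data entry, and Section 4.3.2.1 also requires the baseline assessments to be complete first.

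On recruitment, Section 4.3.1.2 says: "The PI and other members of the research team will identify eligible patients through electronic medical record (EMR) review". The team must also "receive permission from the patient's oncology clinician(s) before approaching eligible patients".

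The document does not say how the sequence is generated, who generates or uploads the list, who may view it, or whether upcoming assignments are concealed from those who recruit. Section 4.6 limits access to the study database to the research team, and Section 7.4 describes an audit trail of data entries and changes. Neither mentions the allocation list.

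**The concern.** Allocation concealment means that nobody who decides whether and when a patient enters can know the next assignment. It is separate from blinding: a trial that cannot be blinded after assignment, as here, can still be concealed before it. The plan reserves setup to two named roles, and one of them also helps to select patients. A protection against changing an assignment does not protect against knowing it in advance.

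If the next assignment were known, the kind of parent entered could come to differ between arms. The result most exposed is the comparison of CSES change between FACT and waitlist. Section 7.3.4 says of the pilot: "This pilot study is not designed nor powered to detect differences". The same section nevertheless uses the pilot's CSES results to project the effect size for a future efficacy trial, so a distortion would carry forward.

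**Working it through.** The point is textual, so the check sets the sections side by side. The plan's one calculated result, the exact 95% interval for 15 of 20 in Section 7.2, reproduces as 50.9% to 91.3%. Nothing here depends on it.

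**1. Do the roles overlap?** Setup: PI or CRC only (4.3.2.2). Identification of eligible patients: the PI and other team members (4.3.1.2). The overlap is certain for the PI's role if the PI does the setup. For the CRC it cannot be established, because no section says that the CRC identifies, approaches or consents patients.

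**2. What does each safeguard prevent?**

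| Safeguard | Prevents | Prevents foreknowledge? |
|---|---|---|
| Biostatistician confirms the logic (4.3.2.2) | A scheme that malfunctions | No |
| Assignment cannot be altered (4.3.2.2) | Tampering | No |
| Randomisation after baseline entry (4.3.2.1, 4.3.2.2) | Assignment before consent and baseline measures | No: it fixes when the arm is assigned, not what the person who did the setup can see |
| Clinician permission before approach (4.3.1.2) | Approach to patients judged unsuitable | No: it narrows the choice of patients only |
| Database limited to the research team (4.6) | Outside access | No: the PI is in the team |
| Audit trail (7.4) | Unrecorded data changes | No: viewing the list is not mentioned |

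**3. Is there discretion before randomisation?** Yes, at several points.
- Section 3.2.4 excludes patients on the investigator's opinion about comorbid disease.
- Section 4.7 removes participants who meet any exclusion criterion, and replaces those who leave before randomisation.
- Section 7.2 says: "The number of eligible patients per month is higher, however we consider factors that typically lead to deferred enrollment/consent". Not every eligible patient is therefore entered.
- Stage is read from the EMR at screening (4.3.3), so a patient's randomisation stratum can be known before approach.

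**4. Which results are exposed?**
- *CSES comparison.* Section 7.3.4 does not say in so many words that the comparison is between arms. Sections 1.1 and 1.3 do compare with the waitlist, so that is the natural reading.
- *Acceptability rate.* It is measured in the FACT arm only (7.2), against this rule in Section 7.1: "If the percentage of patients who report the intervention is acceptable is 75% or higher, the intervention will be considered for future testing". Foreknowledge could affect it only through who enters that arm. Generally favourable recruitment could move it even with perfect concealment.

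**5. Can the bias be sized?** No. The documents give no input for how many entries might be affected or by how much. The background noise can be stated. Section 4.1 says: "This is a two-arm, randomized controlled trial of 40 patients with cancer who are parents of minor children". At 1:1 that is 20 per arm. With complete data, the standard error of a standardised mean difference is about √(2/20) = 0.316 SD. At an assumed true difference of 0.40 SD it is √(2/20 + 0.40²/80) = 0.319 SD. The 95% half-width is then 1.96 × 0.319 = 0.63 SD. A modest selection bias would be small beside this, and could not be seen in the pilot's own data.

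**The case against.** The strongest reply is that this is a reporting gap in a small pilot, and that harm needs steps the documents do not show. Setup may fall to the CRC. Setting up a module is not shown to mean viewing a list, and how REDCap permissions work is outside the documents. Several people identify patients, clinicians must agree, there are two strata, and consent and baseline come before assignment. All of this makes it harder to steer a chosen patient into a known slot. The reasons for deferral in Section 7.2 (tired patients, clinic timetables, medical events) are mostly outside the PI's control. The primary result is a single-arm rate, and the CSES comparison is exploratory.

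Much of this stands. A reader might infer that the PI will see the upcoming assignments, or that both people allowed to do the setup are recruiters. The documents support neither. A reader might also infer that the acceptability result is compromised, but it is barely exposed. Any statement of how much the next trial's power would suffer would rest wholly on invented inputs, so none is offered.

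The reply does not supply the missing protection. The plan goes beyond leaving a detail out: it confines setup to two roles, one of which helps to choose patients. The obstacles listed make exploitation harder, but none conceals the list. That random error is larger does not remove the gap either, because a bias that the data cannot reveal has to be prevented by design.

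**Conclusion.** The point holds as a weakness in allocation concealment that should be corrected. It is not evidence that allocation has been or will be foreseen. It rests on the wording of Sections 4.3.2.2 and 4.3.1.2 and on the absence, in the text available, of any statement about viewing or concealing the list. The front pages were not available to this review.

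The consequence is confined mainly to the exploratory CSES comparison and, through it, the effect size projected for the next trial. That reading takes the comparison to be between arms. The size of any bias cannot be derived. Against a standard error of about 0.32 SD, a modest bias would not dominate the pilot estimate. The reason to act is that the change is cheap and that the present text would not let the investigators report that allocation was concealed.

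**What to change.** Change Section 4.3.2.2 in three respects.

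1. The study biostatistician, or another existing team member with no part in identifying, approaching or consenting patients, generates the stratified allocation list and loads it into REDCap. The CRC could do this only if the CRC does not recruit.
2. A second person who does not recruit confirms that the logic works before data collection. The present plan separates building from checking, and this keeps that separation. Having the statistician do both would lose it.
3. Anyone who identifies, approaches or consents patients (the PI, and the CRC if the CRC recruits) has only the right to randomise after baseline entry and cannot view upcoming assignments. One sentence should say so.

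The cost is that the PI gives up direct control of setup, so a technical fault has to go through the person who holds it. The existing statistician does a little more work, and a second non-recruiter has to be named for the check. The change needs a protocol amendment under Section 8.5. Eligibility, assessments and the intervention are unaffected.
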